9.2 SAMPLE SIZE DETERMINATION

Assuming a true effect size of 0.5, a number of 50 participants per arm will provide 80% power to see an effect with a one-sided type I error of 0.05. Thus, the goal is to have 50 evaluable participants per arm in Part A. Allowing for about 20% of the participants randomized not completing 12 weeks of treatment, approximately 125 participants will be randomized to Part A of the study.

In Part B, 50 participants per treatment arm will provide 80% power for an effect size of 0.5 and a one-sided type I error of 0.05. Allowing for about 25% of the participants randomized not completing 12 weeks of treatment, the goal is to have approximately 200 participants over all three dose groups, leading to 50 evaluable participants per treatment arm. In case of an unexpectedly high proportion of participants not completing 12 weeks of treatment (i.e. more than 25%), the number of randomized participants may be increased to achieve 150 patients completing 12 weeks of treatment.

These 200 participants will be recruited outside Japan. In addition to these 200 participants, approximately 20 participants will be recruited in Japan, leading to approximately additional 5 evaluable participants per treatment arm. The primary analysis will be based on all participants recruited outside Japan and in Japan and will be performed when all patients from outside Japan and in Japan complete the study.

Based on data from previously conducted studies in negative symptoms, the standard deviation for the change from baseline in the BNSS Avolition/Apathy Subscale (consisting of the sum of the two items 'Avolition/Apathy: Behavior' and 'Avolition/Apathy: Internal Experience') at Week 12 is about 2.8. Hence, an effect size of 0.5 translates to a reduction (versus placebo) of 1.4 points for the primary endpoint. With an anticipated sample size of 50 participants per arm, statistical significance at the one-sided type I error of 0.05, any observed reductions (versus placebo) by

approximately 0.92 or more points is expected to be statistically significant. For these calculations, the BNSS items are assumed to be rated on a 7-point (0–6) scale, with anchor points ranging from the symptom's being absent (0) to severe (6).

9.3 POPULATIONS FOR ANALYSES

For purposes of analysis, the following populations are defined in Table 7.

Table 7 Analysis Populations

Population	Description
Modified intent-to-treat (ITT)	All randomized participants who have received at least one dose of study drug will be included in the efficacy population.
Per-protocol	All randomized participants who finished 12 weeks of treatment without any major protocol violations and acceptable compliance
Safety	Same as modified ITT population.
Pharmacokinetic	All participants who have received at least one dose of study drug and who have data from at least one post-dose sample will be included in the PK analysis population. Participants will be excluded from the PK analysis population if they significantly violate the inclusion or exclusion criteria, deviate significantly from the protocol, or if data are unavailable or incomplete that may influence the PK analysis. Excluded cases will be documented together with the reason for exclusion. All decisions on exclusions from the analysis will be made prior to database closure.

9.4 STATISTICAL ANALYSES

9.4.1 Demographics and Baseline Characteristics

Demographic information and baseline characteristics will be summarized for all participants randomized. These summaries will be provided for the Safety Population. Summaries will be shown by randomized treatment arm.

9.4.2 Efficacy Analyses

The primary and secondary efficacy analyses will be based on the efficacy population defined in Table 7.

For the primary analysis of the primary endpoint, the model $Y_{ijk} = \mu + b_i + \tau_k + t_j + (\tau t)_{kj} + \epsilon_{ijk}$ will be used. Therein Y_{ijk} denotes the change from baseline in participant i at visit j, μ denotes the general mean, τ_k is the fixed effect of treatment k, t_j is the fixed effect of visit j, and b_i is the baseline value of the variable analyzed for participant i. The model also includes the treatment-by-visit interactions $(\tau t)_{kj}$. The random errors ϵ_{ijk} are assumed to be independent across different participants, while within each participant an unspecified

covariance structure will be modelled. Albeit not mentioned in the model equation, factors other than baseline used for stratification at the time of randomization will be added to the model. Baseline of the variable analyzed will be included as a continuous covariate.

Least squares means per treatment arm as well as visit will be reported with 2-sided 90% confidence intervals in alignment with assumptions for the sample size considerations. Likewise, at each visit, differences between each active treatment arm and placebo will be estimated and also reported with 2-sided 90% confidence intervals. The comparison at Week 12 will be used to test the statistical hypothesis described in Section 9.1.

Analysis methods for efficacy endpoints are summarized in Table 8.

Table 8 Efficacy Statistical Analysis Methods

Endpoint Statistical Analysis Methods Primary: Change from baseline at Week 12 in the Repeated Measures Model as described BNSS avolition/apathy subscore (sum of in Section 9.4.2. items "behavior" and "internal experience") Secondary: CGI-I and CGI-I negative symptoms scores • Percent responders and percent deteriorating CGI-S and CGI-S negative symptoms scores Change from baseline in PANSS total and Similar models as described in Section 9.4.2 will be used for change from symptom factor scores baseline endpoints of approximately Change from baseline in BNSS total and continuous variables (e.g., PANSS, subscores BNSS, DPAS, etc). Change from baseline in DPAS scores Incidence, nature and severity of AEs AEs will be presented as frequency tables with the number and percentage of Incidence, nature and severity of SAEs participants experiencing AEs. Incidence, nature and severity of treatment Summary statistics of raw values as well discontinuations due to AEs as changes from baseline will be Change from baseline in vital signs presented for continuous safety endpoints. Change from baseline in electrocardiogram Laboratory abnormalities will be presented (ECG) intervals: heart rate, PQ (PR), QRS, as frequency tables with the number and QT, RR and QTcF along with information on percentage of participants experiencing T- and U-waves these. Incidence of laboratory abnormalities, based on hematology, clinical chemistry, coagulation and urinalysis test results Concentration per time point To evaluate the pharmacokinetics (PK) of AUCss of RO6889450 and, if feasible, of RO6889450 and RO6889450-derived RO6889450-derived metabolite(s) metabolite(s). C_{max} of RO6889450 and, if feasible, of RO6889450-derived metabolite(s) Other PK parameters as appropriate

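### Part B's primary model shares one baseline slope across all visits although only Week 12 is tested; a baseline-by-visit term would be a cheap safeguard

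*Protocol*

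**What the plan says.** Protocol Section 9.4.2 models change from baseline as a general mean plus baseline, treatment, visit, treatment-by-visit and error, with an unspecified covariance within participant. The baseline term carries a participant index but no visit index: "Baseline of the variable analyzed will be included as a continuous covariate". The section adds that "factors other than baseline used for stratification at the time of randomization will be added to the model". No baseline-by-visit term is named. The Week 12 comparison from this model is the test of the hypothesis in Section 9.1, and differences are reported with two-sided 90% intervals. Table 8 assigns similar models to the continuous secondary change endpoints.

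Section 9.2 sets the planning figures: "Assuming a true effect size of 0.5, a number of 50 participants per arm will provide 80% power", an SD of change that "at Week 12 is about 2.8", and "an effect size of 0.5 translates to a reduction (versus placebo) of 1.4 points for the primary endpoint". For Part B it plans "Allowing for about 25% of the participants randomized not completing 12 weeks of treatment".

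The point concerns Part B only. The SAP supplied covers Part A, which stopped after 27 participants were randomized. SAP Sections 4 and 4.5 make its efficacy analysis descriptive, with no model or test of the endpoint. SAP Section 1 says Part B will have its own analysis document, which is not among the documents here.

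**The concern.** In Part B the BNSS is rated after baseline at Days 14, 28, 42, 56 and 84 during treatment (Protocol Table 2). Four of the five visits that determine the common slope therefore precede the one that is tested. If change depends on baseline more strongly, or less strongly, at Week 12 than earlier, the fitted slope is a compromise that does not fit Week 12.

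Two consequences can follow. First, some baseline-related variation stays in the Week 12 residual, which costs precision. Second, participants who leave early have the Week 12 assessments done at termination (Table 2, note 2), so a Day 84 rating is not generally available for them and the model in effect predicts it, partly through the baseline slope. If the baseline severity of those who leave differs by arm, a slope that is wrong at Week 12 no longer cancels between arms.

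The contrast affected is the primary one. Because Section 9.1 tests the higher dose first, it also decides whether the lower dose is tested.

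**Working it through.** **The plan's own figures.** Inputs from Section 9.2: difference 1.4, SD 2.8, one-sided alpha 0.05, 50 per arm.
- Effect size: 1.4 / 2.8 = 0.5. Power at 50 per arm: 80.4% (normal), 79.9% (noncentral t). The plan says 80%.
- Smallest significant difference: 1.645 × 2.8 × √(2/50) = 0.921. The plan says "approximately 0.92 or more points is expected to be statistically significant".
- Randomized: 100 / 0.80 = 125 (Part A) and 150 / 0.75 = 200 (Part B).

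All of these reproduce, and none is affected by this point.

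**Why both conditions are needed for bias.** Let g be the common slope, g12 the true slope at Week 12, and d the between-arm difference in mean baseline among those still observed. To first order the Week 12 bias is (g12 − g) × d, partly offset by the unstructured covariance. It is zero if slopes are equal (g12 = g) or if dropout leaves baseline balanced (d = 0). Reversing the sign of d reverses the bias.

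**Simulation.** One active arm versus placebo, 200 / 3 ≈ 67 randomized per arm, five visits, Week 12 SD 2.8, true effect −1.4, REML with unstructured covariance, 1,200 trials per row. Assumptions not in the documents:
- baseline SD 2.0 (1.5 in the last two rows);
- SD rising from 1.8 to 2.8 over visits;
- residual correlation 0.7 between adjacent visits;
- slopes as listed;
- where dropout depends on baseline, a log-odds of 1 per baseline SD;
- total dropout of about 25-30%.

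Positive bias is against active. Each pair is common slope / baseline-by-visit; the ratio is common over by-visit.

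| True slopes, Day 14 to 84 | Dropout and baseline | Bias | 90% half-width | Ratio | Power % |
|---|---|---|---|---|---|
| equal, −0.4 | unrelated | 0.01 / 0.01 | 0.858 / 0.861 | 0.997 | 82.2 / 82.5 |
| moderate, −0.2 to −0.5 | unrelated | 0.01 / 0.01 | 0.849 / 0.839 | 1.012 | 83.2 / 84.1 |
| moderate | active arm only | 0.13 / 0.02 | 0.862 / 0.859 | 1.004 | 76.9 / 83.5 |
| moderate | opposite by arm | 0.25 / 0.02 | 0.877 / 0.897 | 0.978 | 68.7 / 80.8 |
| large, −0.1 to −0.7 | unrelated | 0.00 / 0.01 | 0.824 / 0.778 | 1.059 | 85.1 / 88.7 |
| large | active arm only | 0.23 / 0.02 | 0.836 / 0.797 | 1.050 | 73.6 / 87.3 |
| large | opposite by arm | 0.45 / 0.01 | 0.849 / 0.832 | 1.021 | 58.3 / 86.0 |
| moderate, baseline SD 1.5 | active arm only | 0.10 / 0.02 | 0.884 / 0.886 | 0.997 | 76.9 / 81.1 |
| large, baseline SD 1.5 | active arm only | 0.18 / 0.02 | 0.871 / 0.853 | 1.021 | 73.0 / 84.0 |

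The Monte Carlo error of a bias is about 0.55 / √1200 = 0.016, so the 0.01-0.02 left with baseline-by-visit is noise. Standard errors had no small-sample correction and coverage was about 88% for both models when unbiased, so the comparisons should be read as relative.

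**Large-sample check (40,000 per arm).** With equal slopes and opposite-direction dropout, both models show the same negligible bias (about −0.02). The standard error scaled to 67 per arm is 0.5368 with the common slope and 0.5563 with the interaction: 0.5563 / 0.5368 = 1.036. This is the largest precision cost of the interaction seen.

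**Weaker dropout dependence.** A separate simulation used log-odds ±0.3 per baseline point, about 23% missing and 300 trials per scenario. It gave −1.30 with the common slope and −1.42 with the interaction (Monte Carlo SE 0.03), a bias of about 0.10. The variance was about 5% higher with the interaction, or √1.05 − 1 ≈ 2.5% in width.

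**If the bias favours active.** With a standard error of about 0.53 (0.877 / 1.66), a bias of 0.10 to 0.25 is 0.19 to 0.47 standard errors. By normal approximation, one-sided type I error becomes 1 − Φ(1.645 − 0.19) ≈ 7% to 1 − Φ(1.645 − 0.47) ≈ 12%.

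**The case against.** The strongest reply is that a prespecified common-slope model with treatment-by-visit and unstructured covariance is coherent, and that nothing in the documents shows the conditions for harm. That largely stands. No visit-specific slopes, SDs or correlations are given, and nothing indicates that severity drives dropout differently by arm. Section 7.1.2 withdraws participants hospitalized for worsening psychosis or judged at imminent risk of relapse. That makes severity-related dropout plausible but says nothing about a difference between arms.

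Nor can slope change be taken for granted. The slope of change on baseline is r × (SD at visit / SD at baseline) − 1. If r falls from 0.75 to 0.50 while the SD ratio rises from 1.0 to 1.5, the slope is −0.25 both times.

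Three stronger readings are tempting and are not supported:
- A reader might infer that the common slope generally widens the Week 12 interval. It does not with equal slopes, and with moderate slope change and opposite-direction dropout its interval is about 2% narrower, though around a biased estimate.
- A reader might infer that the planned 25% dropout itself produces bias. When dropout was unrelated to baseline, bias was 0.00-0.01 in every slope pattern.
- A reader might infer that the secondary models omit the BNSS randomization stratum. If baseline means that of the variable analysed, then in a PANSS or DPAS model the BNSS stratum is itself one of the "factors other than baseline used for stratification at the time of randomization will be added to the model", so Section 9.4.2 would include it.

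It is also fair that the separate Part B analysis document may already contain the interaction. The protocol does not.

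**Conclusion.** The point holds in a limited form, for Part B only. As written, the primary model imposes one baseline slope on all visits while only Week 12 is tested.

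The precision cost is nil if slopes are equal, about 1% in half-width for moderate slope change and 5-6% for large change. Bias arises only if slopes differ between visits and dropout also depends on baseline severity differently by arm. It is then roughly 0.1 to 0.25 points under moderate slope change, which is 7% to 18% of the planned 1.4 (0.1 / 1.4 and 0.25 / 1.4). Under the stronger dropout dependence in the table, power falls to about 77% or 69%, against 84% or 81% with baseline-by-visit. Weaker dependence gives smaller bias. The direction follows the arm that loses the more severe participants and cannot be known in advance.

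Both conditions are assumptions. This is a cheap improvement to the model; the sample size figures stand.

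**What to change.** Add a baseline-by-visit interaction to the Section 9.4.2 model, and to the similar models for secondary change endpoints. State it in both the protocol and the Part B analysis document. Do this before unblinding, which means before any of the optional Part B interim analyses in Section 9.5, because these unblind sponsor team members at treatment-group level.

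The text change is one sentence in each document. The model gains four slope parameters (five visit-specific slopes instead of one) with about 200 participants. The interval may be about 2% wider under opposite-direction dropout with moderate slope change, and was 3.6% wider in the least favourable case examined. In return, the Week 12 contrast no longer depends on the slopes being equal across visits.

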3. OBJECTIVES AND ENDPOINTS

The objectives and corresponding endpoints are provided in Table 4.

Table 4 Objectives and Endpoints

Objectives **Endpoints** Primary Part A: To compare the efficacy of Part A & B: Change from baseline at Week 12 in QD of RO6889450 as monotherapy with the Brief Negative Symptoms Scale (BNSS) placebo on negative symptoms in patients avolition/apathy subscore (sum of items with schizophrenia or schizoaffective "behavior" and "internal experience"). disorder. Part B: To compare the efficacy of QD of RO6889450 as add-on therapy with placebo on negative symptoms in patients with schizophrenia or schizoaffective disorder. Secondary To compare the effect of RO6889450 with Change from baseline in CGI-S and CGI-S placebo on: negative symptoms scores Clinical Global Impression Severity CGI-I and CGI-I negative symptoms scores (CGI-S) and change (CGI-I) (overall and negative symptoms)

Objectives	Endpoints
To compare the effect of RO6889450 with placebo on: Symptoms of schizophrenia or schizoaffective disorder as assessed with the Positive and Negative Syndrome Scale (PANSS), BNSS, and Defeatist Performance Attitude Scale (DPAS)	Change from baseline in PANSS total and symptom factor scores Change from baseline in BNSS total and subscores Change from baseline in DPAS scores
To compare the safety and tolerability of 12 weeks of treatment with RO6889450 as monotherapy (Part A) or add-on therapy with placebo (Part B).	 Incidence, nature, and severity of AEs Incidence, nature, and severity of SAEs Incidence, nature, and severity of treatment discontinuations due to AEs Change from baseline in vital signs Change from baseline in ECG intervals: heart rate, PQ (PR), QRS, QT, RR and QTcF along with information on T- and U-waves Incidence of laboratory abnormalities, based on hematology, clinical chemistry, coagulation and urinalysis test results Change from baseline in C-SSRS and extrapyramidal symptom rating scale, abbreviated (ESRS-A)
To evaluate the PK of RO6889450 and RO6889450-derived metabolite(s).	 Concentration per time point AUC_{ss} of RO6889450 and, if feasible, of RO6889450-derived metabolite(s) C_{max} of RO6889450 and, if feasible, of RO6889450-derived metabolite(s) Other PK parameters as appropriate
Tertiary/Exploratory	

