8.1.1.3 Clinical Global Impression Scales

The CGI rating scales are tools used to evaluate both the severity of illness and change from baseline (Guy 1976). The CGI-S reflects the severity of illness on a 7-point scale ranging from no symptoms (1) to very severe (7). The CGI-I is used to assess the clinical change as compared to symptoms at baseline using a 7-point scale, ranging from very much improved (1) to very much worse (7). In this study, overall clinical status will be evaluated with the CGI-S and CGI-I. Overall global impression of negative symptoms will be assessed using the CGI-S and CGI-I for negative symptoms (Haro et al 2003).

Only in part A: At screening, clinicians will gather information from the patient's past psychiatric history, caregiver feedback, and clinical judgement to determine two to three prodromal or MTS historically associated with a signal of the patient's relapse. The patient's MTS (including frequency, intensity, interference with daily function or family life, and other salient consequences) will be recorded and these symptoms evaluated using the CGI-S MTS. At post-baseline visits, the clinician will use the MTS description and re-evaluate the MTS using the CGI-S and CGI-I. This re-assessment of the patient's prodromal symptoms will support with the ongoing clinical evaluation of relapse risk.

It takes approximately 15 to 20 minutes to complete all CGI-I and CGI-S scales.

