## **4. STATISTICAL METHODS**

The final analysis of data from the trial will be performed separately for **Part A** and **Part B**. This TDSA describes the analyses for **Part A**.

Data for study **Part A** will be listed and summarized descriptively. No formal hypothesis test will be performed.

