##### **CGI-I and CGI-I NS**

The CGI-I, a 7-point scale rating, is used to assess the clinical changes as compared to symptoms at baseline. The scale requests an assessment by how much, compared to baseline, the condition of the participant has changed (see [Appendix 5](#)). Values range from 1 (very much improved) to 7 (very much worse) where the value 0 corresponds to 'Not assessed', which will be excluded from any analyses. The values 1 to 7 will be centered prior to analysis so that 0 becomes 'no change' and the values -3 and +3 correspond to 'very much improved' and 'very much worse', respectively.

The CGI-I NS is very similar to the CGI-I and will be analyzed in the similar manner.

In study **Part A** CGI-I along with CGI-I NS will be evaluated at Day 14, Day 28, Day 42, Day 56, Day 70, Day 84 /EOT, Day 112 (FU) by an experienced clinician. All assessments will be assigned to analysis study days as described for the primary endpoint.

The The CGI-I and CGI-I NS scores will be summarized. There is not baseline value for CGI-I and CGI-I NS, therefore no change from baseline can be derived.

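### Protocol Table 8 gives CGI-I and CGI-I NS only responder and deterioration percentages, without cut-offs or a full-scale comparison, although the declared endpoint is the score

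*Protocol*

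**What the plan says.** Protocol Section 3, Table 4, declares the secondary endpoint as "CGI-I and CGI-I negative symptoms scores". Section 8.1.1.3 describes the instrument: "The CGI-I is used to assess the clinical change as compared to symptoms at baseline using a 7-point scale", from 1 (very much improved) to 7 (very much worse).

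Protocol Section 9.4.2, Table 8, sets against it "Percent responders and percent deteriorating". Neither term is defined in either document, and no test or model is named. For other secondary endpoints the table says "Similar models as described in Section 9.4.2 will be used for change from" baseline in approximately continuous variables, with PANSS, BNSS and DPAS as examples. CGI-I has no baseline value, as SAP Section 4.5.2.1 notes, so it does not fall under that wording.

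The SAP covers Part A only. Its Section 4.5.2.1 keeps the whole scale: "The values 1 to 7 will be centered prior to analysis so that 0 becomes 'no change", with -3 and +3 at the ends. Its output is descriptive: "CGI-I and CGI-I NS scores will be summarized". Section 4 adds "No formal hypothesis test will be performed". SAP Section 1 assigns Part B to a separate document, which is not among those supplied.

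**The concern.** For Part B the protocol is the only plan available, and there the declared endpoint and the listed analysis differ: a seven-category score is declared, and two percentages are analysed. Cutting an ordered scale once treats every rating on the same side of the cut as equal, which costs precision. CGI-I NS is the clinician's global rating of the symptom domain that the primary endpoint measures, so it is a natural check on the primary result.

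The missing cut-offs are a second problem. A responder could mean a rating of 2 or better, or of 3 or better, and deterioration could start at 5 or at 6. Protocol Section 9.5 allows Part B interim analyses in which sponsor team members are unblinded at group level, so the definitions should be fixed before then.

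**Working it through.** **1. The plan's own figure.** Protocol Section 9.2 uses effect size 0.5, SD 2.8, one-sided 0.05 and 80% power for the BNSS avolition/apathy subscore. n per arm = 2 × ((1.645 + 0.842)/0.5)² = 49.5, so 50; power at 50 per arm is 0.804. The critical difference is 1.645 × 2.8 × √(2/50) = 0.92, as stated. With dropout, 100/0.80 = 125 and 150/0.75 = 200. All reproduce. No sample size or power is given for CGI-I.

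**2. Assumptions for CGI-I (not from the documents).** A latent normal scale cut into seven categories; a shift of 0.5 SD, borrowed from the primary endpoint, with 0.3 as a check; four placebo distributions over categories 1 to 7, in percent:
- A: 1/8/25/45/15/5/1
- B: 1/6/23/55/12/2/1
- C: 3/17/30/35/10/4/1
- D: 6/26/33/25/7/2/1

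**3. Formulas, per arm, one-sided 0.05, 80% power.**
- All categories (tie-corrected Wilcoxon): n = (1.645 + 0.842)² × (1 − Σp̄³) / (6 × (P − 0.5)²), where P is the probability that an active rating is better than a placebo rating, counting ties as half, and p̄ is the mean category probability.
- One cut: n = [1.645√(2p̄(1−p̄)) + 0.842√(p₁(1−p₁) + p₀(1−p₀))]² / (p₁ − p₀)², where p̄ is now the mean of the two rates.

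**4. Worked case, C, shift 0.5.** P = 0.629 and 1 − Σp̄³ = 0.931, so n = 6.18 × 0.931 / (6 × 0.129²) = 58. A responder at 2 or better moves from 20.0% to 36.6%: n = (1.645 × 0.637 + 0.842 × 0.626)² / 0.166² = 90. The ratio, before rounding, is 1.56.

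**5. All four distributions, shift 0.5.** Entries are n per arm, with the ratio to all seven categories in brackets.

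| Placebo | All seven | Responder ≤2 | Responder ≤3 | Deteriorating ≥5 | Both cuts: ≤3 / 4 / ≥5 | Both cuts: ≤2 / 3–4 / ≥5 |
|---|---|---|---|---|---|---|
| A | 59 | 125 (2.14) | 79 (1.35) | 122 (2.07) | 66 (1.13) | 73 (1.25) |
| B | 61 | 142 (2.32) | 81 (1.32) | 151 (2.47) | 67 (1.10) | 83 (1.36) |
| C | 58 | 90 (1.56) | 80 (1.39) | 151 (2.62) | 73 (1.27) | 69 (1.20) |
| D | 58 | 80 (1.38) | 92 (1.58) | 201 (3.48) | 88 (1.52) | 70 (1.21) |

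If deterioration starts at 6, the ratio is 5.0 to 8.9. The two right-hand columns use responder, neither and deteriorating as one three-category ordinal outcome.

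**6. Sensitivity, shift 0.3.** Responder cuts give ratios of 1.37 to 2.57, deteriorating at 5 or worse 1.93 to 3.07, and both cuts jointly 1.08 to 1.45. The pattern is the same.

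**7. Information kept by one cut of a normal variable.** φ(c)²/(p(1−p)) is 64% at the median, 49% at a 20% rate and 34% at a 10% rate.

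**The case against.** Table 8 only summarises methods, and the Part B analysis plan may hold the cut-offs and a full-scale analysis. The one SAP available keeps the full score, so the gap is shown for the protocol and not for every plan of this trial. That stands, but the protocol text should still not point to percentages alone.

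Several stronger readings are tempting and are not supported:

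- That most of the information is discarded. One cut near the median keeps about 64%. The loss passes half only when the response rate is below about 20%, and two cuts used jointly keep more than one.
- That about 60% more participants are needed. This is close to one special case: a single near-median cut against an idealised continuous score (79 against 50 per arm, a ratio of 1.58). The documents give no CGI-I rates and no cut-offs, and only the BNSS subscore is powered.
- That the percentages are formally tested, or that they leave out the roughly 25% expected not to complete. Table 8 names no test. Section 9.4.2 puts the secondary efficacy analyses in the modified ITT population, and footnote 2 to the Part B schedule asks for the Week 12 assessments at early discontinuation. Table 8 is silent on visits and covariates, and silence does not show exclusion.
- That the two percentages overlap. Improvement and deterioration are disjoint categories.
- That CGI-S is dichotomised too. The columns of Table 8 are interleaved in the extracted text. CGI-S is declared as change from baseline and may already fall under the model-based row. The same damage makes the match of the percentages to CGI-I probable, not certain.

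It is also fair that the Section 9.4.2 model cannot be carried over unchanged, because it uses a baseline value of the analysed variable and CGI-I has none.

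**Conclusion.** The point holds in limited form. In the supplied Part B plan, CGI-I and CGI-I NS are declared as scores, but the only listed method is two undefined percentages. The direction of the loss is the same in every distribution and at every cut examined. Its size depends on the assumptions in the working: at a 0.5 SD shift, roughly 30% to 130% more participants for one responder cut, at least about twice as many for deterioration alone, and about 10% to 50% more for the two cuts jointly.

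The consequence is lower precision and power for a secondary endpoint that stands outside the dose-testing sequence of Protocol Section 9.1. Neither the primary analysis nor the trial's size is affected. Part A is not affected either: it is descriptive, and 27 participants were randomized. The change is worth making because it is cheap.

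**What to change.** In Table 8 and the Part B analysis plan:

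- Make a full-scale comparison the main analysis of CGI-I and CGI-I NS. Use either a repeated measures proportional-odds model, or a repeated measures model on the centred score with treatment, visit, treatment-by-visit and the stratification factors. Use baseline CGI-S (for CGI-I) or CGI-S NS (for CGI-I NS) as the covariate in place of the missing baseline.
- Keep the responder and deterioration percentages as supportive description, and state both cut-offs before any unblinded look at Part B data.
- Confirm that CGI-S and CGI-S NS are analysed as change from baseline, as Table 4 states. Nothing more is needed there.

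This needs no new data. The cost is the wording, slightly more analysis work, and a main summary that is less directly interpretable than a percentage, which the retained percentages offset.
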